8.3 Determination of Sample Size and Accrual Rate

8.3.1 Sample Size and Power Estimate

The sample size for this single-arm phase II study is based upon the anticipated degree of improvement in the primary clinical hypothesis (i.e. local-regional control rate) at 12 months after completing all protocol treatment. The null hypothesis is that 60% of patients treated may achieve local-regional control after treatment on the study. Patients treated for advanced-stage

nonmelanomatous skin cancers typically achieve 50-60% local-regional control with radiation therapy alone. The alternative hypothesis is that 80% of the patients will obtain local-regional control at 12 months from the end of protocol therapy. This goal for local-regional control is justifiable as the current study includes radiation therapy, which is known to be effective against advanced BCC, in combination with vismodegib, also known to have high efficacy against BCC when administered alone.

Sample Size Justification: With accrual of 24 evaluable patients, this test will have 81% power to detect an increase in the overall proportion of patients achieving local-regional control assuming a directional level of significance of 0.10 based upon a one sample exact binomial test. It is anticipated that accrual will be completed in 12-18 months, with each patient treated for approximately 5.5 months and then followed for 12 months after completing protocol therapy. The total study duration is expected to be about 3 years.

8.3.2 Replacement Policy

Patients who drop-out before starting radiation therapy will be replaced. In addition, patients who come off study before completing at least 75% of radiation therapy given concurrently with vismodegib without grade ≥ 3 toxicity will be replaced. The frequency of each of these events will be reported and reasons for replacement reviewed.

8.3.3 Accrual estimates

The multi-center study expects to accrue 1-2 patients per month over a 2 year period. The UCSF radiation oncology program sees approximately 15 patients with locally advanced BCC of the head and neck per year. Approximately 8 patients have inoperable carcinomas or have a medical contraindication to surgery. UCSF will accrue 5-6 patients per year for a total of approximately 10 patients.

8.4 Interim Analysis for Safety and Stopping Rules

An interim analysis for safety will be performed once 5 patients have been treated on study and completed all drug and radiation-based protocol therapy. This will occur approximately 7-8 months after the start of accrual assuming 2 patients are enrolled per month and protocol therapy is completed in about 5.5 months. After the fifth patient completes radiation therapy, accrual will be temporarily stopped in order to perform this interim analysis. Thus no additional patients will start radiation therapy during the evaluation interval that overlaps with the treatment period for patients included in the interim analysis. During the conduct of this study, toxicity will also be evaluated weekly so that any unacceptable toxicity can be identified early. If there is no reason to stop accrual (as defined below), the remainder of the 19 patients will be recruited.

Stopping rules: Acceptable occurrence of toxicity is defined as the discontinuation of treatment in $\leq 40\%$ of patients (2 of 5 patients who discontinue protocol treatment, having completed $< 75\%$ of planned radiation therapy) and the proportion of patients with grade 4-5 toxicity is $\leq 20\%$.

Accrual of the final 19 patients will be determined by the results of the interim analysis.

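### Section 8.4 triggers the safety interim on five completers but judges them on early discontinuation, and at its own accrual rate the pause gates about 8–10 patients, not 19

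*Combined protocol and SAP*

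**What the plan says.** All of the following is in Section 8.4 unless another place is named.

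- **Trigger.** "An interim analysis for safety will be performed once 5 patients have been treated on study and completed all drug and radiation-based protocol therapy".
- **Timing.** "This will occur approximately 7-8 months after the start of accrual assuming 2 patients are enrolled per month", with protocol therapy taking about 5.5 months.
- **Pause.** "After the fifth patient completes radiation therapy, accrual will be temporarily stopped in order to perform this interim analysis". From this the section concludes: "Thus no additional patients will start radiation therapy during the evaluation interval". The sentence then limits that interval to the part overlapping the treatment period of the patients in the interim analysis.
- **Rule.** Toxicity is acceptable if at most 40% discontinue, explained as "2 of 5 patients who discontinue protocol treatment, having completed" less than 75% of planned RT, and if at most 20% have grade 4–5 toxicity.
- **What the interim decides.** If there is no reason to stop, "the remainder of the 19 patients will be recruited"; and "Accrual of the final 19 patients will be determined by the results of the interim analysis".
- **Parallel review.** "toxicity will also be evaluated weekly so that any unacceptable toxicity can be identified early".

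Elsewhere, Section 3.2 sets the target as 24 evaluable patients. Section 8.3.2 replaces patients who leave before RT, or before 75% of RT without grade 3 or higher toxicity. Section 8.3.3 expects 1–2 patients per month over two years, while Sections 3.6.1 and 8.3.1 expect accrual in 12–18 months.

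**The concern.** Two things in Section 8.4 do not fit together.

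First, the group that triggers the look is defined by having completed treatment, yet one of the two limits applied to it counts failure to complete. That limit is not incidental: stopping for toxicity before 75% of RT is the trial's feasibility endpoint (Sections 2.2 and 8.2).

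Second, the pause comes only when the fifth patient ends RT, more than five months after that patient enrolled, and nothing caps enrolment at five in the meantime. The pause therefore cannot hold back all of the 19 patients whose accrual it is said to decide.

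At stake is the only stopping rule in the plan with numerical limits. As written, two careful readers could apply different rules to the same early patients, and the section implies that more patients sit behind the gate than its own timing allows. The efficacy test is not affected.

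**Working it through.** **1. Trigger against rule.** A patient who has completed all drug and RT has had more than 75% of planned RT. Among five such patients, the number who stopped below 75% is 0 by definition, so the first limit cannot be crossed on the literal reading. The same definition excludes a patient who died on treatment or stopped early for grade 4 toxicity, so the grade 4–5 limit is also assessed on a selected group.

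If early stoppers do count, the limits operate as follows (the true rates are illustrative; the documents give none).

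- Discontinuation limit, crossed at 3 or more of 5: P(Bin(5, p) ≥ 3) = 0.163, 0.317 and 0.500 at p = 0.3, 0.4 and 0.5.
- Grade 4–5 limit, crossed at 2 or more of 5: P(Bin(5, p) ≥ 2) = 0.081, 0.263 and 0.472 at p = 0.1, 0.2 and 0.3.

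**2. The plan's own timing.** At 2 per month the fifth patient enters at month 2.0–2.5. Adding 5.5 months gives 7.5–8.0; adding 21 weeks (4.83 months, Section 3.4) gives 6.8–7.3. The stated 7–8 months reproduces.

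**3. Enrolled at the pause.** At Section 8.4's rate, 2 × 7 = 14 to 2 × 8 = 16. The other rows use the same method: even entry, pause at the fifth entry plus 21 weeks or 5.5 months. Remaining = 24 − enrolled, with no replacements.

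| Rate per month | Source | Enrolled | Beyond first five | Remaining of 24 |
|---|---|---|---|---|
| 2 | 8.4; 24 in 12 months | 14–16 | 9–11 | 8–10 |
| 1.33 | 24 in 18 months | 11–12 | 6–7 | 12–13 |
| 1 | 8.3.3, lower end | 9–10 | 4–5 | 14–15 |

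If the trigger really needs five completers, the look comes later. With an assumed 20% not completing, 5/0.8 = 6.25 entries are needed, so the pause falls at 6.25/2 + 5.5 = 8.6 months, with about 17 enrolled at 2 per month.

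**4. Replacements.** The documents give no replacement rate, so 10% and 20% are assumed. Total enrolment for 24 evaluable is then 24/0.9 ≈ 27 or 24/0.8 = 30.

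- At 2 per month, 11–13 (27 − 16 to 27 − 14) or 14–16 (30 − 16 to 30 − 14) remain.
- At 1 per month, 17–18 or 20–21 remain.

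**5. RT status at the pause, 2 per month.** Entries are half a month (2.17 weeks) apart. RT lasts 7 weeks (Table 5.1), or up to 9 with the ten treatment days of breaks in Section 5.6. With equal induction, the patients beyond the fifth who have started RT are those who entered within that window: 7/2.17 = 3.2, so 3; 9/2.17 = 4.1, so 4.

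- Started RT: 8–9, of whom 3–4 are beyond the first five.
- Enrolled but not yet on RT: between 14 − 9 = 5 and 16 − 8 = 8.

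The length of the pause is not given. If it lasted 4 weeks, 1–2 of those 5–8 would reach their RT start during it.

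**The case against.** The best defence is that the intent is clear enough. A rule that mentions 2 of 5 patients discontinuing must expect some of the five to discontinue, so completed should be read as finished or came off. The 19 is simply 24 minus 5 in evaluable units, and speaking of the remainder of the 19 concedes that some are already enrolled. At 1 per month with an assumed 20% replaced, 20–21 patients are still to come. The sentence on RT starts is qualified and covers only the interval overlapping treatment of the interim patients. Toxicity is also watched in other ways:

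- weekly evaluation (Section 8.4);
- Site Committee review (weekly in Section 7.8, monthly in Appendix 9);
- six-weekly DSMC discussion of serious events;
- notification when grade 3 or 4 rates exceed the brochure or label;
- the Study Chair's ability, contemplated in Appendix 9, to stop enrolment at any time.

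Much of this stands. A reader might infer that the discontinuation limit is simply void, or that patients have no effective safety stop. The documents support neither: the parenthesis points to early stoppers being counted, and the other reviews operate. A reader might equally infer that the grade 4–5 limit is untouched by the wording of the trigger. That is not supported either, because the literal trigger removes deaths and early toxicity stops from it.

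What remains is that intent has to be guessed. The text never says that early stoppers count, nor whether a patient replaced under Section 8.3.2 stays among the five. At Section 8.4's own rate the remainder is below 19 even with 20% replaced. The qualifier does not rescue the RT-start sentence. If it means the time while the five are under treatment, 3–4 others have already started RT by the pause. If it means the pause itself, stopping accrual does not hold patients already in induction. None of the other reviews is a numerical boundary.

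**Conclusion.** The point holds as a conflict in wording with a measurable consequence. On the literal trigger the discontinuation limit is always 0 of 5 and the grade 4–5 limit is assessed on a selected group. On the likely intended reading the discontinuation limit is crossed with probability 16–50% at assumed true rates of 30–50%. The same limit thus differs between never and up to one in two, depending on a definition that the plan leaves open.

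The statement that the interim decides accrual of the final 19 does not match the section's own figures: about 8–10 of 24 remain at 2 per month and 14–15 at 1 per month, before replacements. The accrual pause alone does not ensure that no further patients start RT.

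The counts assume even accrual from opening and equal induction. Start-up lag or replacements would change them, and replacements raise the number remaining. The continuing reviews limit the practical harm, so this is a correction to make to the plan, not evidence that safety monitoring is absent.

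**What to change.** Amend Section 8.4 as follows.

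1. Define the interim cohort, for both limits, as the first five patients to start concurrent therapy, analysed when the fifth of them has completed or stopped RT.
2. State that early stoppers and deaths in that cohort count, whether or not the patient is replaced under Section 8.3.2, and that each cohort patient's induction events count toward the grade 4–5 limit.
3. Keep the existing 40% and 20% limits.
4. Replace 19 with the number not yet enrolled at the pause.
5. Reconcile the sentence on RT starts with the induction schedule and the delay wording in Sections 5.1, 6.1.2.3 and 6.1.6. If a hold on RT starts is meant, say so and give its length. Which clinical rule applies is for the sponsor to settle, not this review.

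The grade 4–5 limit should not be moved to all treated patients. Two events among five is 40% and crosses the limit; the same two among 14–16 is 12.5–14% and does not. A present stop could thus become a continue, diluted by patients who have had induction drug only.

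The cost is amendment wording: no new patients, visits, data or looks. One limit of this definition is that events in patients who never start concurrent therapy fall outside the five. They remain covered by the safety analysis in Section 8.6 and the continuing reviews.

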3.4 Duration of Therapy

In the absence of treatment delays due to adverse events, treatment may continue for approximately 21 weeks or until:

- Disease progression
- Inter-current illness that prevents further administration of treatment
- Unacceptable adverse event(s)
- Patients decides to withdraw from the study
- Significant patient non-compliance with protocol
- General or specific changes in the patient's condition render the patient unacceptable for further treatment in the judgment of the investigator.

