4.2 Radiation Therapy

The administration of radiation therapy is outlined in section 5.2.

There will be expected radiation related toxicities; very likely toxicities are mucositis, mouth dryness or changes in taste and/or smell that may be permanent, thick saliva, hoarseness, tanning or redness and/or irritation of the skin in the head and neck area being treated with radiation, ear pain and/or pressure, fatigue, weight loss, permanent hair loss in the area treated with radiation (face, chin, neck), and hypersensitivity of teeth and/or loss of teeth or cavities in the teeth, if strict dental care is not followed.

Serious but less likely toxicities are decreases in function of the thyroid gland that may require thyroid replacement therapy; serious damage to the spinal cord, nerves in the neck, jawbone, larynx, skin, or other parts of the head and neck that may require surgical intervention and may

be life threatening; temporary pain or scarring around nerves in the shoulder that could cause numbness and/or weakness; breathing problems; difficulty with swallowing and eating, possibility of inhaling food and/or liquids into the lungs which could result in pneumonia; serious ear infections and/or hearing loss; damage to the spinal cord leading to permanent weakness and/or symptoms like a stroke; loss of hearing; and decreased vision.

In general, the anticipated toxicities from the combination of vismodegib and radiation therapy should not be overlapping in a synergistic fashion with the possible exception of wound healing. It is possible that the side effects of radiation therapy which are related to wound healing may be intensified in the presence of vismodegib. In the absence of any further surgical procedures given after the combined therapy, it is not expected that there should be serious additional toxicity related to wound healing over that expected from a typical standard-of-care radiation therapy course, although these types of effects will be tracked carefully as part of this study protocol.

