6.1.3 End-of-Treatment Study Procedures

To be completed within 8 – 12 weeks of the last dose of study drug.

- Physical examination including weight
- Vital signs
- Performance status
- Evaluation of adverse events
- Concomitant medications
- Skindex-16 survey
- Laboratory assessments
 - Hematology
 - Serum chemistries
- Urine or serum pregnancy tests within 4 weeks after completion of radiation therapy - if a woman of childbearing age
- Disease assessment
- Imaging (CT or MRI) of head and neck for tumor assessment
- CT chest or chest x-ray – if clinically indicated
- For externally visible tumors
 - Bidimensional measurements of externally visible tumor dimension
 - Digital photography of target lesion(s)
 - Description of the lesion
 - Tumor biopsy – as needed to confirm progression

If biopsy results are confirmatory of persistent cancer, the patient may be offered salvage surgery as indicated. This would result in discontinuation from the study. Post-salvage follow-up may be conducted by UCSF investigators with separate consent by the patient.

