8.2 Study Endpoints

Primary Endpoint:

- The proportion of patients with local-regional control at 12 months from protocol therapy completion, defined as complete or partial response, with absence of PD (see section 7.2) within the irradiated PTV.

Secondary Endpoints:

- Estimate of the probability of PFS and OS 12 months after protocol therapy completion. PFS is measured until disease recurrence or death due to any cause, whichever occurs first.
- Number and attribution of all adverse events (including vital signs, physical findings, and clinical laboratory results, CTCAE, v 4.0) in patients who receive any amount of study drug and radiation therapy.
- For each toxicity, the maximum occurring grade will be tabulated for each patient. The results will be summarized by toxicities observed during vismodegib treatment alone, during concurrent vismodegib with radiation therapy, for 3 months immediately following the completion of protocol therapy and for up to 12 months after completion of protocol therapy. The focus will be on the proportion of patients experiencing \geq grade 3 toxicity during each of these intervals.
- Proportion of patients experiencing Grade 4-5 adverse events assessed to be definitely, probably, or possibly related to the induction or concurrent treatment components of the protocol regimen (that is not definitely related to disease progression).
- Proportion of patients discontinuing treatment due to toxicity during the concurrent administration of vismodegib and radiation therapy. For this endpoint, discontinuation is defined as $<$ 75% of planned radiation therapy delivered.
- Response rate per RECIST criteria in patients who complete initial combined therapy of the primary site and regionally involved areas in subjects with measurable disease prior to initiation of therapy at 3 months after completion of protocol therapy.
- Proportion of patients with a decrease of BCC within the irradiated PTV after completing all protocol therapy to estimate clinical response to vismodegib and radiation therapy.

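### The only numeric safety check (section 8.4) comes when the fifth patient finishes therapy and is never repeated, so much of the 3-month early-toxicity window in those five patients is not tested against the grade 4-5 limit

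*Combined protocol and SAP*

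**What the plan says.** Section 8.4 sets the trigger: "An interim analysis for safety will be performed once 5 patients have been treated on study and completed all drug and radiation-based protocol therapy". It adds: "After the fifth patient completes radiation therapy, accrual will be temporarily stopped in order to perform this interim analysis". On timing it says: "This will occur approximately 7-8 months after the start of accrual assuming 2 patients are enrolled per month", with about 5.5 months of therapy per patient.

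Toxicity is acceptable if no more than 40% of patients discontinue (under 75% of planned radiation delivered) and no more than 20% have grade 4-5 toxicity. With five patients, the second limit allows one. Section 8.4 gives no data cut-off, no toxicity window and no length for the evaluation interval. It also mentions weekly toxicity evaluation, with no limit attached.

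Elsewhere the period after therapy is treated as a toxicity interval of its own. Section 8.2 summarises toxicity separately "for 3 months immediately following the completion of protocol therapy", section 2.2 makes it an objective, and section 8.5 makes it one of four tabulated stages. Section 4.2 names one possible overlap between the two treatments: "It is possible that the side effects of radiation therapy which are related to wound healing may be intensified in the presence of vismodegib".

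Adverse events are assessed weekly during radiation (section 6.1.2.3). Table 6.1 then shows no assessment until the End of Treatment visit at weeks 29-33, for which section 6.1.3 says: "To be completed within 8 – 12 weeks of the last dose of study drug".

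**The concern.** The look decides whether the remaining 19 patients are recruited to a new drug-radiation combination. The protocol itself expects some toxicity to appear after radiation ends, and names wound healing as the place where the two treatments might interact. Yet the single numeric test is made at the moment when the fifth patient has no post-radiation follow-up and the others have only what slow accrual happens to give them.

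A regimen that is tolerable during treatment but causes excess severe toxicity in the following weeks could pass, and no later step in section 8.4 puts these five patients against the limit again.

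**Working it through.** **Inputs.** Section 8.4: 2 patients per month, 5.5 months of therapy, limit of at most 1 of 5. Section 8.3.3: "The multi-center study expects to accrue 1-2 patients per month over a 2 year period"; 24 patients over 24 months is 1 per month. Sections 2.2 and 8.2: 3-month window, so 5 × 3 = 15 patient-months. Section 6.1.3: visit at 8-12 weeks, or 1.84-2.76 months.

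**Reproducing the stated timing.** With even spacing at 2 per month, patients enter at 0, 0.5, 1, 1.5 and 2 months. The fifth finishes at 2 + 5.5 = 7.5 months, or 8.0 if the first patient enters at month 0.5. This matches the stated 7-8 months and leaves room for a lag of at most about half a month. Section 3.4 gives a shorter course ("treatment may continue for approximately 21 weeks or until", or 4.83 months). That moves the look to 6.83 months but does not change the follow-up below, which depends only on the spacing between patients.

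**Post-radiation follow-up at the look, patients 1 to 5**

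| Accrual | Months since radiation | Window observed (capped at 3 months each) | Past 8 weeks | Full 3 months |
|---|---|---|---|---|
| 2/month | 2, 1.5, 1, 0.5, 0 | 5 of 15 (33%) | 1 of 5 | 0 of 5 |
| 2/month, 0.5-month lag | 2.5, 2, 1.5, 1, 0.5 | 7.5 of 15 (50%) | 2 of 5 | 0 of 5 |
| 1/month | 4, 3, 2, 1, 0 | 9 of 15 (60%) | 3 of 5 | 2 of 5 |

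**Effect on the test.** The documents give no event rates, so these are assumptions: a 10% on-treatment grade 4-5 risk and a further risk q of 10%, 20% or 30%, spread evenly over 3 months. For a patient with f months of follow-up (capped at 3), p = 1 − 0.90 × (1 − q × f/3). The look passes if at most one of the five has an event.

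Example at q = 20%:
- Look at 2 per month: p = 0.22, 0.19, 0.16, 0.13, 0.10; P(at most 1) = 0.82.
- All five followed to 12 weeks: p = 1 − 0.90 × (1 − 0.20 × 2.76/3) = 0.266; 0.734⁵ + 5 × 0.266 × 0.734⁴ = 0.60.
- All five followed to 8 weeks: p = 0.210; P = 0.72.

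| Probability of passing | q = 10% | q = 20% | q = 30% |
|---|---|---|---|
| Look, 2/month, no lag | 87% | 82% | 76% |
| Look, 1/month, no lag | 83% | 72% | 61% |
| Events through an 8-week visit | 83% | 72% | 60% |
| Events through a 12-week visit | 77% | 60% | 43% |

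At 1 per month, a tabulation at an 8-week visit has almost the same pass rate as the look itself. The gain is clear at 2 per month, or when the visit falls nearer 12 weeks.

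**False flags.** At q = 10% the cumulative 3-month risk is 1 − 0.90 × 0.90 = 19%, inside the 20% limit. Counting the whole window, the limit is exceeded with probability 1 − (0.81⁵ + 5 × 0.19 × 0.81⁴) = 24%, against 13% at the 2-per-month look.

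**The case against.** A reader might infer that the data are cut at the fifth patient's last fraction, so that post-radiation grade 4-5 events do not count at all. On the same assumed 10% on-treatment risk the look would then pass 92% of the time. The text does not support this. Section 8.4 sets a trigger and an accrual pause, not a data cut, and its grade 4-5 limit carries no time restriction. The related endpoint in section 2.3.2 covers therapy and follow-up.

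Other safeguards continue. Grade 4-5 events are life-threatening or fatal and would generally be serious, and sites report all serious events within one business day of awareness (section 7.9), without waiting for the next visit. The DSMC discusses serious events every six weeks (section 7.8). Appendix 9 requires notice to the DSMC if grade 3-4 rates exceed the reference rates, and provides for the Study Chair stopping enrolment at any time. Section 4.2 also says that serious extra wound-healing toxicity is not expected without further surgery, and that such effects will be tracked. All this stands: individual severe events should become known. None of it, however, applies the section 8.4 limit or reopens the decision that the limit governs.

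A second look may also come late for accrual. At a steady 2 per month without a pause, about 20 patients would be enrolled by then. Fewer would have been irradiated. The fifth patient's visit falls at 7.5 + 1.84 to 7.5 + 2.76 = 9.3-10.3 months. Radiation starts about 5.5 − 1.6 (7 weeks) = 3.9 months after entry, so only those entered by about 5.5-6.4 months, 11-13 patients, would have started it. The re-check can still inform the decision for about half the trial.

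**Conclusion.** The concern holds in a limited form. Section 8.4 requires no post-radiation observation at its only numeric check and never re-applies the grade 4-5 limit to those five patients. The unobserved share of the 3-month window is 67% at 2 per month and 40% at 1 per month, given even spacing and a look made as soon as the fifth patient finishes. A half-month lag at 2 per month reduces it to 50%.

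The loss of sensitivity is material at 2 per month (82% against 60% passing at q = 20% with a 12-week visit) and small at 1 per month if the visit falls at 8 weeks. These pass rates rest on assumed risks and an even spread of events. The follow-up shares use the protocol's own figures. This is a cheap improvement to safety monitoring and does not show that the existing look is invalid.

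**What to change.** Keep the look and its timing. Add two statements to section 8.4:

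- All grade 4-5 events known at the look count toward the limit, whenever they occurred.
- Once the fifth patient has had the End of Treatment visit, the grade 4-5 limit is re-tabulated for these five patients with events through that visit, and the accrual decision is reviewed again if the limit is exceeded.

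Only the grade 4-5 limit needs repeating. The discontinuation limit depends on how much radiation was delivered, which cannot change after radiation ends.

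The cost is one more tabulation of data already collected at a scheduled visit, and a possible second accrual pause 8-12 weeks after the first look. It also raises the chance of flagging a regimen whose true risk is within 20% (about 24% at a 19% cumulative risk). That is why exceeding the limit should prompt a review and not an automatic stop.
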